16.4. The electronic database (integerafrica)

For the purpose of monitoring and auditing the study, source documentation will consist of the laboratory report and the hard-copy CRFs developed and maintained by the investigator. Data recorded on source documents will be entered using electronic forms using an electronic data capture and management system provided by integerafrica. The hard-copy CRFs will be entered onto the electronic database by data-enterers at the clinic. integerafrica will design a tailor-made database with electronic forms that mirror the hard-copy CRFs. The electronic database will be a web-based research platform developed and maintained by integerafrica (www.integerafrica.org). The database will be ICH-GCP compliant. A subcontract will be awarded to integerafrica for the purpose of database design and maintenance. The portal is an easy-to-use web-enabled tool that assists medical researchers to track, analyze, and report on an individual case level. The platform allows researchers to enter data from multiple sites using one centralized database and provides tools for real-time data analysis. The architecture is developed according to clinical workflows and chronological procedures. Data are validated at the point of data entry. Multimedia data formats (chest radiographs, CT/MRI scans, ultrasound images or photographs) can be uploaded on the platform, allowing storage of complete clinical records. Training tools and support pathways are installed within the web-portal. The section Frequently Asked Questions (FAQ) serves as a guidance for the use of the platform. After login onto the TBIRIS website, the researchers have access to a variety of information regarding the study. In the download center, documents such as paper CRFs, informed consent forms, clinical guidelines, the study protocol, SOPs, study information sheets for patients, and patient education sheets can be made available. All data can be exported for further analysis in Excel format. The platform is available 24/7. The platform implements appropriate administrative, physical and technical safeguards to ensure the confidentiality, integrity and security of electronic health information. This database is being used in the EDCTP-funded eKhayaVac trial of the novel TB vaccine MVA85A being conducted in Khayelitsha (www.ekhayaovac.org), the Pan African Pulmonary Hypertension Cohort study (www.papuco.org) and the Registro Latinoamericano de Hipertensión Pulmonar (www.relahp.org).

integerafrica technology architecture

The main information technology design philosophy is an end-to-end solution approach, with specific focus on security, scalability, performance, and ease-of-use. The system is designed

to utilize the very best technology available to provide for a cost-effective and sustainable research environment in an African context. This is made possible by the extensive use of open-source technology. The system is built with hundreds of open-source components consisting of thousands of programs and millions of lines of code. The system architecture integrates five main components. 1) Devices: The system supports a wide variety of devices including mobile phones, tablet computers, laptops and desktop computers. Any computer with a browser and internet connection can use the system. 2) Browsers: The development of modern browsers have made it possible to develop and deliver much more powerful and secure web-based solutions for clients. The browser in many cases has replaced the reliance on propriety software and hardware. 3) Interfaces: The system supports any connection to the internet. It is designed for low bandwidth use without sacrificing a rich user experience. A connection speed as low as 512kbps is sufficient. The extensive use of caching technology throughout the system makes this possible. 4) User Experience: The user has access to a host of tools to manage research data with ease, securely. 5) Data Capture: The system allows for the secure capture of research data, geo-location data, imaging, videos, audio files and patient appointments. 6) Support: Training and support is provided in to study personnel. This is supplemented by online support in the form of training videos, frequently asked questions pages as well as a 24/7 online support request framework. 7) Security: Strict password policies, user access control logic, data encryption and SSL connection encryption are all in place to provide a secure user environment. 8) Data Storage: All data storage, as well as on- and off-site backup are provided. 9) Visualization: Real time project summary data is provided and well as basic analysis. All data can be visualized various formats including maps, charts and graphs. 10) Data Export: Data can be searched and selected from and exported in XLS or CSV format for further analysis, or sharing of results. 11) Reports: Custom reports can be generated and exported as PDF files or printed. 12) System Backend Firewall: As security is paramount, the first line of defense on web based systems is the use of various layers of firewall technology to guard against unauthorized intrusion. Both hardware and software firewalls are employed. 13) Server Security: Various industry standard, enterprise security policies are implemented and maintained across the various servers and server software components. 14) Cache and Proxy Servers: The advanced caching and proxy technology used for back-end optimization allows for fast, powerful and scalable solutions. Caching of various server components allows for the exponential increase in users, and fast responsive user experience managing research data online. 15) Web Server: The system utilizes Apache web-server technology that in 2009 was the first web-server to surpass the 100 million website milestone. 16) Application Server: On the application server side the system uses PHP and the Drupal framework to create fast and secure customized research solutions. The Drupal framework is a worldwide open source collaboration of more than 16000 developers in 228 countries. 17) Database Server: The system relies on the world's most popular database MySQL. 18) Backups: The backup policy extends to real-time RAID backups, On- and Off- Site data backups as well as database replication where needed.

The platform is accessible at www.TBIRIS.org and hosted at one of the world's most reliable hosting companies Hetzner online in Germany. Maintenance of the platform includes: daily server quick checks, daily security audits, and implementation of Drupal update releases, Drupal minor security updates, server security updates, server backups, annual SSL renewals. The main lines of our support services are: user and centre registration process guidance, user

personal data maintenance, online training for users on individual level using Skype, and online support requests for all the how-to items.

16.5. Data quality and completeness checking

Automated data checking mechanisms will be installed into the electronic database. Certain variables will be validated at the point of data entry, while data with reference values will be displayed in color codes according to reference range. Different field types (integer, decimal, range integer, range decimal, date, text field, text select list (drop down menu, multi-select, radio button for polar variables) will also be implemented to reduce errors at entry level.

The database is aware of the participant's position in the trial and will only allow certain procedures as per study protocol. Double electronic data entry will occur (hard-copy CRFs will be entered independently by two data enterers) and any discrepant entry will be flagged and/or the electronic record cannot be saved. Various list views allow for visual validation of data at entry and upon saving of the record. Every patient record is in a human readable format which allows the electronic record to be used as a electronic patient card. The database includes a complete check that gives a percentage of completeness of each record and the names of the missing fields. This information is available at the list view modules after login.

Additional data quality checking will be done (and documented) on every CRF by the study team. Any data errors or missing data detected will be corrected on both the hard-copy CRF and on the electronic database by the study doctor, who will sign and date changes on the hard-copy CRF and a system will be put in place to ensure all changes to the hard-copy CRFs are made onto the electronic database within one week of the change being made. Data entry and review will be co-ordinated by the Data Management Team at UCT with advice from the team at ITM (see section 20.1). Further details of the Data Management plan will be detailed in a specific standard operating procedure (SOP).

16.6. Records retention

The sponsor and the investigator will retain trial essential documents for at least 15 years after trial completion. The electronic database will be retained for an indefinite period.

17. Study monitoring, audit and inspection

17.1. Trial monitor

The trial will be monitored by a monitor that is subcontracted by the sponsor UCT to undertake monitoring. The monitor will be [name]. She will perform a study initiation visit and thereafter monitoring visits every two months with an average of 3 hours per patient for source document verification as well as monitoring the regulatory binder, ethics committee communication, SAE reporting and informed consent documents.

17.2. Data and safety monitoring board (DSMB)

The trial will be monitored by an independent DSMB. This DSMB will be comprised of 3

independent internationally-recognized HIV-TB researchers and an independent statistician (subcontracted by UCT). The DSMB will be appointed by the sponsor before trial recruitment starts and will also have its first meeting with the investigators (via conference call) to make necessary modifications to the draft DSMB charter prepared by the investigators and approve the final charter before recruitment starts. The charter will specify the stopping rules for the trial that will be based on DSMB review of the blinded and/or unblinded data. It will also specify the specific data to be reviewed by the DSMB and whether or not these data needs to be presented to the DSMB in a blinded or unblinded manner or that the data summaries may be partly concealed.

Once the trial is underway, the DSMB will meet twice during the trial. The first meeting will occur after 80 participants (~33%) have been enrolled and completed follow-up and the second after 160 participants (~66%) have completed follow-up. The DSMB may also decide to convene an unscheduled DSMB review if warranted by safety or data quality concerns. The data for review will be prepared by the independent statistician.

Data including the following will be prepared for DSMB review:

- Study recruitment by month
- Eligibility violations
- Baseline characteristics
- Protocol violations
- Data completeness report
- Primary and certain secondary endpoint summaries
- Summary of adverse events (ACTG grade 3 and 4)
- Deaths on the trial

The task of the DSMB will thus be to review study recruitment, data quality and drug safety and advise the sponsor of major safety issues and data quality issues. The DSMB may advise that trial enrollment should be stopped based on significant safety concerns. However, although the DSMB will have access to the primary endpoint data (paradoxical TB-IRIS events) decisions regarding whether to stop the trial will not be based on this data. The DSMB may choose to review the efficacy data in a blinded fashion (following the DSMB charter). The DSMB meetings during the trial will take place via conference call and will include an open part when the investigators are present and update the DSMB members on unblinded aspects of the study. This will be followed by a closed part after the investigators have left the meeting when blinded data is reviewed and discussed and the DSMB recommendations are made.

The DSMB report and recommendations will be sent to the sponsor (the University of Cape Town represented by the Deputy Dean of the Faculty of Health Sciences at University of Cape Town). The sponsor will then make the decision based on the DSMB recommendations to continue the trial or to prematurely stop enrollment or to implement any alternative recommendation of the DSMB.

18. Adverse event grading, recording and reporting

18.1. Adverse event grading and recording

The ACTG adverse event grading system will be used (see addendum 2: DIVISION OF AIDS TABLE FOR GRADING THE SEVERITY OF ADULT AND PEDIATRIC ADVERSE EVENTS VERSION 1.0, DECEMBER, 2004; CLARIFICATION AUGUST 2009).

All grade 1, 2, 3 and 4 clinical and laboratory adverse events will be recorded on the CRF and the adverse event log in each patients study folder.

18.2. Serious adverse event reporting

All adverse drug reactions, serious adverse events and deaths will be reported to the UCT Human Research Ethics Committee and the Medicines Control Council according to these bodies' guidelines on reporting as detailed below. Reporting to the sponsor's representative (UCT Faculty of Health Sciences Deputy Dean for Research) will be done at the same time that reporting is done to the Ethics Committee and to the DSMB. A cumulative report of all serious adverse events and deaths will be presented at each Trial Steering Committee meeting.

18.2.1. Reporting to UCT Faculty of Health Sciences Human Research Ethics Committee (UCT FHS HREC)

The study medical officer, study co-ordinator or principal investigator will report to the UCT FHS HREC using a cover letter and the UCT FHS HREC standard form (fhs008):

Definitions

- Unanticipated event: Must be all three of the following: a) unexpected, b) related to the research and c) harmful to participants or others
- Unexpected adverse event: Any of the following applies: a) Inconsistent with current information given to participants, b) inconsistent with current risk information in the protocol application, c) occurring more frequently than anticipated
- Serious Adverse Event: Results in any of the following: a) death, b) life-threatening incident, c) hospitalization, d) disability, e) congenital abnormality, f) requires medical or surgical intervention, g) inadvertent disclosure of confidential information.

Reporting

- Unanticipated problems will be reported within seven calendar days of being aware the occurrence.
- Adverse Drug Reactions (Fatal and life-threatening, Unexpected): As soon as possible, but no later than 7 calendar days after first learning about the event.
- Adverse Drug Reactions (Non-fatal, Serious, Unexpected): As soon as possible but no later than 15 calendar days.

- Adverse Drug Reactions (Expected): Only if occurring at significantly higher frequency or severity than expected and then within 15 calendar days.
- New Information that might impact the Conduct of a Clinical Trial: 3 Calendar days of first learning of its occurrence.

We will mail all Ethics Committee reports to:

The Chair, University of Cape Town Human Research Ethics Committee, [name].

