18.2.2. Reporting to the Medicine Control Council of South Africa

Reporting of adverse events to the MCC will be done according to the document entitled Medicines Control Council: Reporting Adverse Drug Reactions in South Africa (May 2003). Section 5 refers to reporting of adverse events in clinical trials (Appendix C). The events will be reported using a cover letter and a copy of the form submitted to the ethics committee that provides a detailed narrative explaining the event. Expedited reporting is not appropriate if the event is not related to the study product. A named investigator will sign the report and submit a hard copy by mail as well as fax a copy to the MCC.

Key timelines for reporting:

a) Deaths:

All deaths will be reported within 7 days of becoming aware of the event, unless the death is unexpected and due to a serious adverse event, when it will be reported within 3 days as per the study protocol.

b) Adverse Drug Reactions: Fatal or life-threatening, unexpected

MCC requirement: Report as soon as possible but within 7 calendar days.

c) Adverse Drug Reactions: Not fatal or life-threatening, unexpected

Report as soon as possible, but within 15 calendar days.

d) Adverse Drug Reactions: Expected, but change in nature, severity or frequency, or new risk factor identified

Report within 15 calendar days.

e) Information which changes the risk-benefit assessment of trial:

Report within 3 calendar days.

f) Serious adverse events:

Report as part of the 6-monthly progress report in line listing format.

g) Non-serious adverse events:

Report as part of the 6-monthly progress report in line listing format.

We will mail all MCC reports to:

Medicines Control Council Clinical Trials Unit

[name]

[name]

Pretoria

0001

19. Ethical considerations

Ethical and regulatory approval

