- Hyperglycaemia (random glucose > 11.1 mmol/l)

- Hypomania/mania
- Depression
- Acne
- Epigastric pain
- Upper gastro- intestinal bleeding
- Cushingoid features
- New oedema
- Avascular bone necrosis

b) Comparison of laboratory safety bloods done at week 2, 4 and 12: sodium, potassium, creatinine, ALT, alkaline phosphatase, total bilirubin, glucose, haemoglobin, white cell count, neutrophil count, total lymphocyte count and platelets. Comparison of medians will be performed at each time point using the Wilcoxon rank sum test. The proportion of participants who develop an ACTG grade 3 or grade 4 abnormality in these blood tests will also be compared using Chi-square test or Fisher exact test (as appropriate).

c) Comparison of week 12 CD4 count and HIV viral load results. Comparison of medians will be performed using the Wilcoxon rank sum test. Proportion of participants with less than $2 \log_{10}$ drop in HIV viral load from screening to week 12 will be compared using the Chi-square test or Fisher exact test (as appropriate). Where screening viral load was too low to ascertain a $2 \log_{10}$ drop then an undetectable viral load at week 12 will be regarded as successful outcome.

d) Comparison of the proportion of participants who are diagnosed with other infections (AIDS-related, bacterial, fungal and viral) and malignancies (Kaposi's sarcoma) will be compared using Chi-square test or Fisher exact test (as appropriate). These will also be presented with individual listing. The proportion with severe infections (classified as any AIDS-defining (WHO stage 4) infection or invasive bacterial infection) will be compared in a separate analysis.

e) The proportion of participants with any clinical ACTG grade 1, 2, 3 and 4 adverse events (AEs) will be compared using Chi-square test or Fisher exact test (as appropriate). A similar comparison will be made for serious adverse events (SAEs) and adverse drug reactions (ADRs) attributed as definite, probably or possibly due to medication (the relationship between ADRs and medication has been determined by the study doctors and categorized as definitely not, unlikely, possibly, probably or definitely related to any medication).

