In addition, a listing of AEs and SAEs categorized using MedDRA will also be presented. AEs and SAEs will be coded using the Medical Dictionary for Regulatory Activities (MedDRA) and will be reported based on MedDRA preferred terms and body systems. All AEs and SAEs will be analyzed based on counts of patients with a specific category and not on counts of individual adverse events.

All safety and tolerability analyses will be performed for the 12 week trial period, as well as a separate analysis restricted to the first 4 weeks from randomization. The reason for performing these analyses at 4 and 12 weeks, is that certain participants may commence open label corticosteroid (generally from 2-3 weeks onwards) so the 4 week analysis will exclude most of the safety events related to open label corticosteroid and more directly compare study prednisone versus placebo.

6. Pre-specified subgroup analyses relating to the primary endpoint

A number of pre-specified subgroup analyses of the primary endpoint will be performed using an ITT population. These subgroups will be

- a) Participants with screening CD4 count \leq 50 cells/ μ L
- b) Participants with screening CD4 count $>$ 50 cells/ μ L
- c) Participants with screening HIV viral load $>$ 100,000 copies/ml
- d) Participants with screening HIV viral load \leq 100,000 copies/ml
- e) Participants with microbiologically proven TB (TB culture and/or Xpert)
- f) Participants not diagnosed with rifampicin-resistant TB during follow-up.

7. Analysis of risk factors for TB-IRIS

As a tertiary analysis, we will assess possible risk factors for developing IRIS (age, gender, extrapulmonary TB, lymph node TB, TB diagnosis method, baseline CD4 count, baseline HIV viral load, CD4 count increase at 12 weeks, log HIV viral load decrease at 12 weeks, duration from TB treatment to ART initiation, urine LAM status, baseline CRP, and baseline haemoglobin, neutrophil, white cell counts and Karnofsky score) in addition to treatment arm in multivariable logistic regression model and Cox regression on cause-specific hazards.

8. Missing data and sensitivity analyses

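### SAP 5(e) compares serious adverse events between arms without defining them, and the only definition available (protocol 18.2.1) counts any event needing intervention, including treated TB-IRIS

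*Supplement*

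**What the plan says.** Protocol version 1.4, section 18.2.1, lists seven criteria, any one of which makes an event serious. The first four are death, a life-threatening incident, hospitalization and disability. The rest are "e) congenital abnormality, f) requires medical or surgical intervention, g) inadvertent disclosure of confidential information". The list sits under the heading "18.2.1. Reporting to UCT Faculty of Health Sciences Human Research Ethics Committee (UCT FHS HREC". Criterion f) is not limited to intervention that averts one of the other outcomes, and criterion g) is not a medical outcome.

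No other SAE definition appears. Section 18.2.2, on reporting to the medicines regulator, uses the term undefined. So does SAP section 5(e), which says, after the graded adverse events, "A similar comparison will be made for serious adverse events (SAEs"). The end of SAP section 5 fixes the unit of analysis: "All AEs and SAEs will be analyzed based on counts of patients with a specific category and not on counts of individual adverse events".

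Protocol 13.2 allows open-label corticosteroid for TB-IRIS at the physician's discretion. Protocol 14.1 plans the trial on TB-IRIS in 35% of the placebo arm and 17.5% of the prednisone arm.

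**The concern.** A list written for prompt reporting can afford to be wide. A between-arm comparison cannot, because every participant who qualifies through a minor treated event adds the same outcome as one who died or was admitted. Participants here have advanced HIV and TB, are starting ART and take co-trimoxazole, so events that need some treatment are to be expected in both arms.

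Two things can go wrong. Treated events that are equally common in both arms shrink the difference and reduce power. Treated TB-IRIS works in one direction: if prednisone prevents TB-IRIS, the placebo arm gains SAE cases, and the benefit is counted as better safety. Safety is the fourth objective in protocol 4.1, and a reader of the trial report will give weight to the SAE line.

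**Working it through.** **Figures in the plan.** The documents state no SAE rate and no power for SAEs, so there is no such figure to reproduce. The only planning rates used here are the TB-IRIS rates in protocol 14.1. The 110 per arm stated there is recovered with the continuity-corrected two-proportion formula, but it has no bearing on SAEs.

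**Inputs.**
- 240 randomised 1:1, so at most 120 per arm in the all-patients-treated set (SAP sections 1 and 5).
- Two-sided 5% (SAP section 3; protocol 14.1).
- Assumed: 10% of placebo and 20% of prednisone participants have an event meeting a) to e).
- Assumed: a share *b* of participants in each arm has an event that qualifies only through f), independent of a) to e).
- Assumed: a share *s* of TB-IRIS cases is treated and so meets f), again independent of a) to e).

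**Power formula.** With d = p1 − p0 and p̄ the mean of the two rates:
- s0 = √[2p̄(1 − p̄)/120]
- s1 = √[(p0(1 − p0) + p1(1 − p1))/120]
- power = Φ((d − 1.96·s0)/s1) + Φ((−d − 1.96·s0)/s1)

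For 10% versus 20%: s0 = 0.0461, s1 = 0.0456, and (0.10 − 1.96 × 0.0461)/0.0456 ≈ 0.21. Power is 58%.

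**Step 1: dilution.** The recorded rate becomes 1 − (1 − p)(1 − b), so the difference shrinks to 0.10 × (1 − b).

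| b | Placebo | Prednisone | Power |
|---|---|---|---|
| 0 | 10% | 20% | 58% |
| 10% | 19% | 28% | 38% |
| 20% | 28% | 36% | 26% |
| 50% | 55% | 60% | 12% |
| 90% | 91% | 92% | 6% |

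**Step 2: offset by TB-IRIS.** Take TB-IRIS at 35% and 17.5%, and no other treated-only events. Placebo becomes 1 − 0.90(1 − 0.35s) and prednisone 1 − 0.80(1 − 0.175s). The difference is 0.10 − (0.315 − 0.140)s = 0.10 − 0.175s.

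| s | Placebo | Prednisone |
|---|---|---|
| 0 | 10% | 20% |
| 0.50 | 25.8% | 27.0% |
| 0.75 | 33.6% | 30.5% |
| 1 | 41.5% | 34.0% |

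At s = 0.50 power is about 6%. The difference reaches zero at s = 0.10/0.175 = 0.57, and above that the sign reverses. The last row is an upper bound, because treatment is discretionary.

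**Step 3: does the four-week analysis remove this?** SAP section 5 repeats the safety analyses over the first four weeks, to leave out most events related to open-label corticosteroid. Protocol 3.2 gives a median TB-IRIS onset of 14 days, interquartile range 7 to 25, in the investigators' cohort. If that timing held, about three quarters of TB-IRIS would begin within 28 days and could still enter the four-week SAE count.

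**The case against.** The strongest reply is that the serious harms have their own tests. The SAP compares all-cause hospitalization (4i), all-cause death (4l) and a composite of death, hospitalization or hepatotoxicity (4n), each in both analysis populations. It also compares pre-specified corticosteroid-associated events (5a), grade 3 or 4 laboratory abnormalities (5b), severe infections (5d), and graded clinical adverse events and drug reactions (5e). None of these uses the 18.2.1 list. This stands, and it rules out the inference that the safety objective rests on the SAE comparison. It does not make the SAE line itself interpretable, and life-threatening events and disability have no separate comparison by seriousness.

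Second, the list was written for an ethics committee, and the SAP does not import it. That is correct, so one should not say that the SAP chose to count every treated event. The SAP is silent, and the reporting list is the only definition left to fill the gap. Keeping serious and non-serious events apart in regulator listings (18.2.2), and reviewing each SAE individually in the steering committee (20.2), also suggests that sites may have applied f) narrowly. The documents do not say so.

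Third, a reader might infer that the analysis becomes a tally of treated events. It does not, since the SAP counts participants. Counting participants does not cure the problem, because a single treated event is enough to qualify.

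Fourth, all the magnitudes are assumed. Treated hyperglycaemia or infection could be true prednisone harms and add signal, so the net direction is not known. That also stands. Criterion g) is out of place, but nothing suggests it would add many cases.

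**Conclusion.** The point holds for one secondary safety comparison. Followed literally, the only SAE definition in the documents makes the SAP 5(e) proportion a mixture of grave outcomes, minor treated events and treated TB-IRIS. It can dilute a harm signal and lets efficacy offset it.

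The size cannot be fixed from the documents. Under the assumptions above, the loss runs from moderate (58% to 38% power when 10% have a treated-only event) to nearly complete (6% at 90%). With TB-IRIS at its planned rates, a 10-point excess disappears once about 57% of TB-IRIS cases are treated and counted. It would therefore go too far to conclude that the comparison can hardly show harm: that depends on rates the documents do not give and on how sites applied criterion f). No primary or efficacy result changes. The amendment is worth making, but the trial's conclusions do not hang on it.

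**What to change.** In SAP 5(e), add a definition for the between-arm comparison:
- an SAE is an event meeting criteria a) to e) of protocol 18.2.1, or criterion f) only when the intervention was needed to prevent one of a) to e);
- criterion g) is excluded;
- state whether TB-IRIS events count and, if they do, show the comparison with and without them;
- tabulate SAEs by arm and by seriousness criterion.

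Leave the 18.2.1 list unchanged for ethics-committee reporting. Re-code the recorded SAEs by seriousness criterion before unblinding; SAP section 12 places the SAP ahead of database lock and unblinding, so the order is feasible.

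The cost is a short SAP addition and one blinded re-code. Fewer events will be counted, and the narrower comparison is still not strongly powered: 58% in the scenario assumed here.
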